We will also address the following secondary research questions: How effective is the intervention (advice to use either cytisine or varenicline) in promoting:

- (i) Continuous abstinence over the past month, assessed two months after enrolment?
- (ii) Biochemically verified continuous smoking abstinence for the past six months, assessed seven months after enrolment by a) group allocation (cytisine vs varenicline vs control) and b) by use of recommended medication among those in the intervention arms?

Methods

Study design

This will be a three-arm individually randomised controlled effectiveness trial.

Participants

Participants will be adult smokers residing in the UK who have downloaded and signed up to the Smoke Free app within the past week during the recruitment period. They must be intending to quit smoking in the next month, willing to participate in a 7-month study, be able to provide consent and meet all of the inclusion criteria and none of the exclusion criteria.

Inclusion criteria are:

- (i) aged between 18 and 65 years old (as cytisine is available for prescription in UK to adults 18-65 years old),
- (ii) able to consent,
- (iii) residing in UK,
- (iv) English speaking,
- (v) current cigarette smoker,
- (vi) willing to be followed up by email and complete online questionnaires after two and seven months,
- (vii) interested in making a guit attempt within the next month,
- (viii) have downloaded and signed up to the Smoke Free app within the past week during the recruitment period and have set a quit date no more than 30 days in the future.

Exclusion criteria are:

- (i) current enrolment in another smoking cessation programme/study,
- (ii) current use of smoking cessation medication,
- (iii) varenicline and/or cytisine use in the previous 12 months,
- (iv) pregnant/breastfeeding/planning to get pregnant,
- (v) self-reported moderate/severe renal impairment,
- (vi) treatment for active/latent tuberculosis,
- (vii) experience of a heart attack, stroke or severe angina within the previous two weeks,
- (viii) uncontrolled high blood pressure (> 150 mmHg systolic, > 100 mmHg diastolic),
- (ix) history of seizures.

Eligibility will be assessed via screening questions embedded in the baseline questionnaire. Those who do not meet the inclusion criteria will be provided with information about the best ways to stop smoking (6).

Sample size

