(ii) biochemically-verified continuous smoking abstinence for six months assessed at the 7-month follow-up by a) group allocation (cytisine vs varenicline vs control) and b) by use of recommended medication among those in the intervention arms. Following the Russell Standard, self-reported abstinence will be measured as not having smoked more than five cigarettes for the entire 6-month period preceding the 7-month follow-up (20). Analyses will follow the intention-to-treat principle. This means that all

participants will be analysed in the groups to which they were originally assigned, regardless of whether they completed the study or adhered to the intervention. Multiple imputation will be used to account for missing outcome data (i.e., participants who will be lost to follow-up or did not provide outcome data). As a sensitivity analysis, missing data will be treated as no medication users (for medication use outcomes) and smokers (for smoking cessation outcomes) in the analysis. Self-reported abstinence will be biochemically verified by measuring participants' CO levels via a video call with a researcher. A CO monitor will be sent to participants who self-report abstinence at 7-month follow-up and those with a CO reading of less than 8 parts per million will be classified as abstinent (21, 22).

The baseline questionnaire will assess the following:

Participants' contact details: e-mail address, mobile phone number.

Baseline

Sociodemographic characteristics:

age,

sex (male, female, other),

education (any versus no post-16 qualifications),

financial status (live comfortably, meet needs with little left, just meet basic expenses, do not meet basic expenses (23)),

country of residence (England, Scotland, Wales, Northern Ireland), ethnicity (Asian or Asian British background, Black, Black British, Caribbean or African background, White background, mixed or multiple ethnic groups (e.g., White and Black African or White and Asian), other ethnic group).

Smoking related characteristics:

number of cigarettes smoked per day,

cigarette addiction (first cigarette within 5, 6-30, 31-60 or >60 minutes of waking),

urges to smoke (How much of the time have you felt the urge to smoke a cigarette in the past 24 hours? (not at all, a little of the time, some of the time, a lot of the time, almost all the time, all the time); How strong have the urges been? (no urges, slight, moderate, strong, very strong, extremely strong)(24, 25),

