history of serious quit attempts (never, yes-not in the past year, yes-in the past year),

past and current use of support for smoking cessation (prescription nicotine replacement therapy (NRT), NRT bought over the counter, varenicline, bupropion, cytisine, e-cigarettes, face-to-face behavioural support, telephone support, written self-help materials, website, apps, none, other).

Procedure

Participants will be assessed at enrolment (baseline), two months and seven months after enrolment. Table 1 summarises the schedule of enrolment and follow-up assessments for trial participants.

Potential participants will have downloaded the Smoke Free app within the past week during the recruitment period and only those residing in the UK will see an on-screen message with information about the study and a link to access the baseline questionnaire via a weblink. Those who meet the

eligibility criteria, assessed via the questionnaire and complete the baseline survey, will be automatically randomised to the intervention or control arms.

All questionnaires will be conducted online via REDCap.

Follow-up questionnaires will involve initial contact via email with a link to an online survey. Embedded links will provide the option of responding to the outcome measure assessed in that survey (at 2-month follow-up, medication use; at 7-month follow-up, 6-month continuous abstinence) in a single click. Three attempts will be made one day apart for each follow-up. Follow-up will be attempted at all follow-up points regardless of success at a previous point. A mailing system will be used for the e-mails to enable assessment of whether the e-mail will be (a) delivered versus hard bounce (i.e. permanent delivery problem) versus soft bounce (i.e., temporary delivery problem) and (b) opened.

Invitations and contacts will be structured according to evidence-based methods for maximisation of response rate (26, 27). All invitations will mention incentives for responding.

In order to boost the response rate for the 2-month and 7-month follow-ups, participants who provide their phone number in the baseline questionnaire and consent to receiving text messages and phone calls, will receive first a text message and then a phone call asking them to reply yes or no in order to record their response to the outcomes; medication use at 2-month follow-up and 6-month continuous abstinence at 7-month follow-up.

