Participants who report 6-month continuous abstinence at the 7-month follow-up will be asked to measure their CO levels to verify their abstinence. This will be conducted via a video call with a researcher, using a CO monitor provided by the study team.

Debriefing will involve an e-mail sent after immediate completion of the final follow-up. It will thank participants for their help with the study and provide them with a contact e-mail for further information.

Withdrawal of participants

Participants will be informed that they may withdraw from the study at any time without giving a reason. Unless they withdraw consent, they will be followed up irrespective of smoking outcome or protocol violation. On the basis of the intention-to-treat principle, those who do not respond to endpoint follow-up attempts will be retained in the analyses. Their outcomes will be imputed using multiple imputation (and classified as non-medication users and continuing smokers in a sensitivity analysis). Participants who indicate that they no longer wish to take part in the study will be excluded from the analyses.

Analyses

Primary analyses: Medication use

The primary two comparisons will be as follows:

- Any versus no specific medication recommendation: The first primary analysis will compare the combined medication recommendation arms (varenicline and cytisine) to the control arm (no specific medication recommendation). This analysis will assess whether recommending any medication (varenicline or cytisine) increases medication use.
- Cytisine versus Varenicline recommendation: The second primary analysis
 will compare the cytisine recommendation arm to the varenicline
 recommendation arm among participants randomised to receive a
 medication recommendation. This analysis will determine if there is a
 difference in medication use between the two recommended
 medications.

Logistic regression will be used to model the binary outcome of medication use (yes/no), adjusting for covariates (sociodemographic and smoking-related characteristics at baseline). P-values will be calculated using Wald's test.

The models will include the treatment arms as predictors. To obtain marginal risk ratios (RR) and risk differences (RD) alongside 95% confidence intervals, we will use the *marginaleffects* package in R.

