To account for missing outcome and covariate data, we will use multiple imputation with chained equations (in *mice* package). Imputation models will include experimental group, covariates, self-reported abstinence, and biochemically-validated abstinence. We will assume data are missing at random (MAR), meaning that having missing data on a variable does not depend on the true value of the variable, after accounting for predictor variables included in the imputation model. If less than 10% of data are missing, we will create 5 sets of imputations; otherwise, we will create 20 sets of imputations. Each set will be analysed separately and estimates combined using Rubin's rule.

Secondary analysis: Smoking abstinence outcomes

Above analyses will be repeated for smoking cessation outcomes, defined above in the measures section. As with the primary outcome, multiple imputation using chained equations (the *mice* package in R) will be used to account for missing outcome and covariate data.

Smoking cessation data are often missing not at random, as people who relapse to smoking are generally less likely to complete follow-up. However, the usual way to account for missing not at random, assuming "missing=smoking" (where all individuals with missing follow-up data are assumed to have relapsed to smoking), has been shown to be too extreme in internet-based smoking cessation trials (28). Instead, sensitivity analyses will examine the degree to which violations in the MAR assumption affect results. Multiple imputation with delta-adjustment will be used, with the degree of adjustment ranging from none (delta=0; MAR analysis) to very large (delta=100, approximating the missing=smoking assumption).

	Simple unadjusted complete case and "missing=smoking" analyses will be included in supplementary files as these are often used in meta-analysis.					
	Cost effectiveness					
	First, we will use the smoking cessation outcome directly observed in this trial—comparing the proportion of participants who report having quit smoking across trial arms at follow-up. This will provide a trial-based estimate of the intervention's impact on quitting, which can be used to estimate the potential health benefits (e.g., quality-adjusted life years [QALYs] gained) associated with the intervention.					

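### The imputation models should include phone/text contact status, because the follow-up rule makes it a likely predictor of who responds; leaving it out makes missing-at-random less plausible but does not show bias

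*Protocol*

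**What the plan says.** Under Procedure, follow-up starts by e-mail for everyone, and "Three attempts will be made one day apart for each follow-up". To raise response at both time points, a further step applies to those who gave a phone number at baseline and who "consent to receiving text messages and phone calls, will receive first a text message and then a phone call". The text and call ask for a yes/no answer on medication use at two months, or on six-month abstinence at seven months.

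Under Analyses, Primary analyses: Medication use, missing outcomes and covariates are handled by chained-equation multiple imputation: "Imputation models will include experimental group, covariates, self-reported abstinence, and biochemically-validated abstinence". The outcome model in the same section is described as "adjusting for covariates (sociodemographic and smoking-related characteristics at baseline", which shows what is meant by covariates. Missing-at-random is defined there as missingness that "does not depend on the true value of the variable, after accounting for predictor variables included in the imputation model".

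In the list of baseline measures, "e-mail address, mobile phone number" appear as contact details, apart from the sociodemographic and smoking-related groups. Neither the phone number nor agreement to be texted or called is among the named imputation predictors.

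**The concern.** The protocol conditions its missing-at-random assumption on a named list of predictors. Its own follow-up rule creates a further likely predictor of response, which the list leaves out. If people who agree to be phoned also differ in medication use, or in how they react to the recommendation, they are over-represented among responders, and imputation that ignores this carries the imbalance into the non-responders.

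The abstinence variables in the model may help only partly. A participant who misses the two-month contact will usually lack two-month abstinence as well, and the text and call at two months collect medication use only.

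At stake are the absolute medication-use rates and the primary risk difference, and in some situations the risk ratio. The observed effect on medication use also feeds the indirect cost-effectiveness estimate. Recruitment runs until 876 people have given two-month data and no response rate is stated, so the imputed share is unknown.

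**Working it through.** **The plan's own figure.** With 10% vs 16.8%, two-sided alpha 0.05, 80% power and 2:1 allocation, the arcsine effect size is h = 2·asin(√0.168) − 2·asin(√0.10) = 0.2011. Control n = 1.5 × (1.960 + 0.842)² / h² = 291.01, rounded up to 292; 3 × 292 = 876. The stated sample size reproduces and this point does not affect it.

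**Inputs.** From the Sample size section: control use 10%, recommendation use 16.8%, risk ratio (RR) 1.68, risk difference (RD) 6.8 points. Assumed, because the protocol gives no values: share contactable by phone c = 0.60; response r1 in contactable and r0 in other participants, the same in each arm; control use 12% in contactable and 7% in others (0.6 × 12 + 0.4 × 7 = 10.0%).

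**Formulas.** The contactable share among responders is w = c·r1 / [c·r1 + (1 − c)·r0]. Imputation that ignores contact status targets, in each arm, w·(rate in contactable) + (1 − w)·(rate in others). The full-population value uses c in place of w. Other covariates are left out, so these figures apply to whatever association remains after the listed covariates.

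**Weights.**
- Response 70% vs 35%: w = 0.42 / (0.42 + 0.14) = 0.75.
- Response 50% vs 40%: w = 0.30 / (0.30 + 0.16) = 0.652.

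**Recommendation rates.** Each set averages to 16.8% at c = 0.60.
- Common RR: 20.16% and 11.76%.
- Larger effect in contactable: 22% and 9%.
- Equal RD: 18.8% and 13.8%.

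| Response | Effect pattern | Control | Recommendation | RD (points) | RR | RD bias |
|---|---|---|---|---|---|---|
| any | contact status unrelated to use | 10.00% | 16.80% | 6.80 | 1.68 | 0 |
| 70/35 | common RR | 10.75% | 18.06% | 7.31 | 1.68 | +0.51 |
| 70/35 | larger in contactable | 10.75% | 18.75% | 8.00 | 1.74 | +1.20 |
| 70/35 | equal RD | 10.75% | 17.55% | 6.80 | 1.63 | 0 |
| 50/40 | common RR | 10.26% | 17.24% | 6.98 | 1.68 | +0.18 |
| 50/40 | larger in contactable | 10.26% | 17.48% | 7.22 | 1.70 | +0.42 |

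For example, in row 2: 0.75 × 12 + 0.25 × 7 = 10.75 and 0.75 × 20.16 + 0.25 × 11.76 = 18.06.

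**Wider assumptions.** Take 50–90% contactable, response 80% vs 40–70%, and control use 10% overall.
- Common RR of 1.68, use 1.5–2 times as high in contactable: RD bias 0.03 to 0.76 points, RR unchanged.
- RR 1.8 vs 1.4 or 2.0 vs 1.2, use 1.5 times as high: RD bias 0.06 to 1.73 points; largest RR shift 1.68 to 1.80.
- No true effect, 50% contactable, use twice as high, but response in non-contactable participants 40% in one arm and 60% in the other: a spurious difference of 11.1% vs 10.5%, about 0.6 points.

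**Scale.** The complete-case standard error of the RD at 292 vs 584 is √(0.10 × 0.90/292 + 0.168 × 0.832/584) = 2.34 points. Biases of 0.18, 0.51, 1.20 and 1.73 points are about 0.08, 0.2, 0.5 and 0.7 standard errors.

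**The case against.** The strongest reply is that a predictor of response left out of the model does not by itself break missing-at-random. Contact status must also be related to the outcome given arm and the listed covariates, and nothing in the protocol shows that it is. Those covariates are extensive (demographics, finances, dependence, urges, quit history, past use of support) and may absorb much of any association. This stands, and it limits the point. A reader might infer that the follow-up design defeats the assumption, or that the primary risk difference is biased; the documents support neither.

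If contact status is fixed before allocation it is balanced in expectation. With no effect in either group and the same response pattern in each arm, omitting it creates no spurious difference. This also stands.

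An unseen SAP could add auxiliary variables, and the protocol does not say that its list is closed. That is fair, but the protocol names its predictors and ties missing-at-random to them, so the omission can be raised on this text.

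The planned sensitivity analyses give partial cover. Delta-adjustment is described under the abstinence outcomes, however. For medication use the protocol states only the rule that counts missing as non-use.

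Three further inferences go too far. Nothing shows that contact status is the strongest predictor of response. The phone number is a baseline item, but the text does not say when contact consent is taken or that it is complete. And the argument does not extend to the planned quit date ("have set a quit date no more than 30 days in the future") or to the free or premium app version, since neither determines which contact routes a participant receives.

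**Conclusion.** The point holds as a low-cost improvement, not as a demonstrated bias. The protocol's list omits a variable that its own follow-up rule makes a likely predictor of response, which weakens the case for missing-at-random without refuting it.

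Under the main assumed values the risk difference moves by 0.5 points with the risk ratio unchanged, and by 1.2 points if the effect is larger in contactable participants. A mild response gap with a common risk ratio gives about 0.2 points, and the most extreme combination examined gives 1.73. There is no bias if contact status is unrelated to use given the other predictors. The risk ratio stays unbiased when it is common to both groups and response is equal across arms. Every one of these sizes depends on consent shares, response rates and use rates that the protocol does not give.

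**What to change.** Add one auxiliary variable to the imputation models for medication use and for abstinence: an indicator that the participant gave a phone number and agreed to text or phone contact. Let its association with the outcome differ by arm, either through an arm-by-indicator term or by imputing within arm. With about 29 users expected among 292 control responders (10% × 292), the interaction term may be the more stable choice. State when contact consent is recorded, and make the change before unblinding.

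The cost is a line of protocol or SAP wording and a slightly larger imputation model. No new procedure is needed if consent is already stored with the phone number, which the text implies but does not state. If the indicator proves unrelated to the outcome, little is lost.

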	they complete it within 24 hours. They will also receive a £5 gift voucher
	upon completion of the 7-month follow-up. Participants who report
	abstinence at 7-month follow-up will be offered another £5 gift voucher
	along with a carbon monoxide (CO) monitor for biochemical verification of
	their abstinence.
Randomisation	Those who are eligible and consent to participate in the trial will be
Kanaomisation	randomised after completing the baseline questionnaire. Randomisation will
	be 1:1:1 at individual level with no restrictions (i.e., no blocking) and will be
	generated by an online automated algorithm, which counts to ensure each
	intervention will be displayed equally.
Blinding	Participants cannot be masked to treatment allocation. The investigators will
Dillialing	be blinded to participants' treatment allocation until all data have been
	collected. The trial statistician will have no contact with participants
	throughout the trial and will remain blinded for the analysis.
Intervention	Control
	No specific medication recommendation arm
	Participants in this group will be advised to access the Smoke Free app using
	a unique link provided to participants in the no specific recommendation
	medication arm, where they will receive routine smoking cessation
	behavioural support during their quit attempt. One day after randomisation,
	they will receive an email to remind them to use the Smoke Free app for
	smoking cessation behavioural support. The Smoke Free app is a theory-
	driven and evidence-based smoking cessation app (15). The app is designed
	to support users through the first three months of their quit attempt by
	reinforcing motivation, tracking progress, and highlighting the benefits of a
	smoke-free lifestyle. It incorporates a range of behaviour change techniques,
	including goal setting, reward systems, trigger identification, and coping
	strategies, to help users manage cravings and sustain abstinence (15).

Interventions

Varenicline arm

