Participants in the varenicline arm will receive a digital recommendation and support to use varenicline during their quit attempt, along with information on varenicline's benefits and potential side-effects, instructions for proper use, and guidance on how to obtain the medication either free of charge or with the standard NHS prescription charge. They will also be advised to access the Smoke Free app using a unique link provided to participants in the varenicline arm, where they will receive smoking cessation behavioural support and advice on the benefits of using varenicline during their quit attempt. One day after randomisation, they will receive an email with similar information on varenicline's benefits and potential side-effects, instructions for proper use and guidance for obtaining the medication and a reminder to use the Smoke Free app for smoking cessation behavioural support.

Cytisine arm

Participants in the cytisine arm will receive a similar digital recommendation to use cytisine during their quit attempt, along with information on its benefits and potential side-effects, instructions for proper use and guidance on obtaining the medication either free of charge or with the standard NHS prescription charge. They will also be advised to access the Smoke Free app using a unique link provided to participants in the cytisine arm, where they will receive smoking cessation behavioural support and advice on the benefits of using cytisine during their quit attempt. One day after randomisation, they will receive an email with similar information on cytisine's benefits and potential side-effects, instructions for proper use and guidance for obtaining the medication and a reminder to use the Smoke Free app for smoking cessation behavioural support.

The Smoke Free app will be restricted for participants who enrol in the study, and they will only be able to access it through the unique link based on their group allocation. If participants opt out of the study, they will regain normal access to the Smoke Free app.

Measures

Outcomes

The primary outcome will be percentage of participants reporting medication use (varenicline or cytisine use) at the 2-month follow-up. We will also report percentage of participants reporting varenicline or cytisine use among those recommended one of them at the 2-month follow-up.

Secondary outcomes will be percentage of participants reporting:
(i) continuous abstinence for one month assessed at 2-month follow-up.

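### Randomised participants who opt out are removed from all analyses, which contradicts the protocol's own intention-to-treat definition and discards outcomes already given

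*Protocol*

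**What the plan says.** The Protocol's Outcomes section (under Measures) adopts the principle: "Analyses will follow the intention-to-treat principle". It then defines it: "participants will be analysed in the groups to which they were originally assigned, regardless of whether they completed the study".

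The section Withdrawal of participants (under Procedure) treats three groups differently:

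- **Follow-up in general:** "Unless they withdraw consent, they will be followed up irrespective of smoking outcome or protocol violation".
- **Silent non-responders:** "those who do not respond to endpoint follow-up attempts will be retained in the analyses". Their outcomes are multiply imputed, and a sensitivity analysis counts them as non-users and smokers.
- **People who actively stop:** "Participants who indicate that they no longer wish to take part in the study will be excluded from the analyses".

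Three other places bear on the last rule. Randomisation takes place after consent and the baseline questionnaire, so a later opt-out is a randomised participant. Blinding states: "Participants cannot be masked to treatment allocation". The Interventions text adds: "If participants opt out of the study, they will regain normal access to the Smoke Free app".

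**The concern.** Opting out is one way of not completing the study. The Outcomes section keeps such people in the analysis and the Withdrawal section takes them out. No modified intention-to-treat set is declared, so two analysts could build different primary data sets from the same protocol. This is not a detail left for a statistical analysis plan, because the protocol itself fixes the exclusion.

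The rule has no time limit and is not confined to people who ask for their data to be erased. Three consequences follow:

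1. Someone who reports medication use at month 2 and opts out at month 4 loses an observed primary outcome, and with it the abstinence outcome measured at the same visit.
2. Opt-outs are absent from the sensitivity analysis that would count them as non-users or smokers. The delta-adjusted analysis does not help with the primary outcome, since it is described only for the smoking outcomes.
3. The analysed groups need not be the randomised groups. Participants know their arm, so the decision to leave may depend on it. Both primary comparisons are exposed.

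**Working it through.** **Inputs.** From Sample size: use of 10% in control and 16.8% with a recommendation (RR 1.68, RD 6.8 points), 292 per arm, 876 in total, 80% power, two-sided alpha 0.05, *pwr* package. The protocol gives no opt-out rate and no rate of use among opt-outs, so both are assumptions below.

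**Step 1: the plan's own figure.** With the arcsine effect size that *pwr* uses, h = 2·arcsin√0.168 − 2·arcsin√0.10 = 0.20114. For 2:1 allocation, control n = 1.5 × ((1.960 + 0.8416)/0.20114)² = 291.01, rounded up to 292, or 876 in total. Power at 292 versus 584 is 80.1%. The stated size reproduces, and the fix does not change it.

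**Step 2: effect of exclusion on the estimate.** With true use p, opt-out share w and use u among opt-outs, the rate among those retained is (p − w·u)/(1 − w). For example, w = 10% and u = 0 gives 0.168/0.90 = 18.7%.

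| Opt-out, recommendation / control | Use among opt-outs | Retained rates | RR | RD (points) |
|---|---|---|---|---|
| none | – | 16.8% / 10.0% | 1.68 | 6.8 |
| 5% / 2% | none | 17.7% / 10.2% | 1.73 | 7.5 |
| 10% / 2% | none | 18.7% / 10.2% | 1.83 | 8.5 |
| 10% / 10% | none | 18.7% / 11.1% | 1.68 | 7.6 |
| 2% / 10% | none | 17.1% / 11.1% | 1.54 | 6.0 |
| 10% / 2% | 30% / 10% | 15.3% / 10.0% | 1.53 | 5.3 |
| 10% / 5% | same as own arm | 16.8% / 10.0% | 1.68 | 6.8 |

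The sign depends on which arm loses more people and on whether those people use medication more or less than average.

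**Step 3: false-positive rate.** Let true use be 10% in every arm, all opt-outs non-users, with 584 versus 292 before exclusion. With δ the spurious difference and SE its standard error, the two-sided error is Φ(δ/SE − 1.96) + Φ(−δ/SE − 1.96). It is about 5.0% at 5%/5% opt-out, 5.2% at 5%/2%, 6.9% at 10%/2% and 8.3% at 15%/5%. For cytisine versus varenicline, with both at 16.8% and opt-out of 10%/2%, the spurious RR is 0.98/0.90 = 1.09 and the error about 7.5%.

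**Step 4: loss of observed outcomes.** Recruitment stops once 876 people have given 2-month data. If some of them later opt out and are deleted, the analysed number falls below 876. Power scales as Φ(h·√(194.67·(1 − d)) − 1.96), where 194.67 = 292 × 584/876 and d is the share deleted. It is 79.3% at d = 2%, 78.1% at 5% and 75.9% at 10%.

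**Step 5: what retention plus imputation changes.** Take 10% opt-out before month 2, all non-users, in the recommendation arms. Exclusion gives 18.7%. Imputation under missing at random, from arm and covariates, fills the missing 10% at about the retained rate: 0.90 × 18.7% + 0.10 × 18.7% = 18.7%. The main estimate hardly moves. Counting them as non-users gives 0.90 × 18.67% = 16.8%, but only if they are still in the data set.

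**The case against.** The best defence is a narrower reading. The sentence closes a section on the right to withdraw and may mean only people who withdraw consent to the use of their data, whose removal can be required. The consent pages are not in the copy reviewed, so what participants were promised cannot be checked. That possibility stands, but the text does not say it. The section speaks of withdrawing consent when it ends follow-up and uses a different, broader phrase when it removes people from analyses; neither is defined.

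A second objection is that retention with imputation barely alters the primary estimate. For opt-outs without a 2-month outcome this is right, as Step 5 shows. It does not apply to outcomes observed before opt-out, nor to the sensitivity analysis.

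A reader might also infer that the exclusion inflates the effect in favour of the recommendation, because people who dislike being told to take a drug would leave those arms. The documents do not support that direction. App access is restricted for every enrolled participant, control included, and anyone who opts out gets normal access back. A recommendation can be ignored without leaving the study.

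**Conclusion.** The contradiction is established by the wording alone and rests on no assumed rate. The deletion of 2-month outcomes already given, and the absence of opt-outs from the non-user/smoker sensitivity analysis, follow directly from the rule as written.

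Bias is possible, not shown. It requires opt-outs to differ from those who stay in medication use; when all opt-outs are non-users, the risk ratio shifts only if opt-out also differs between arms. Under that assumption, a 10%-versus-2% imbalance shifts the planned risk ratio to 1.83 or 1.54 according to its direction. At 5% versus 2% the false-positive rate is only about 5.2%.

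It would be tempting to assume opt-out in the recommendation arms alone and quote 0.3 to 1.9 points of inflation (for 2% to 10% opt-out, all non-users) as the cost of the rule. That one-sided worst case lets control lose nobody, and for opt-outs without a 2-month outcome the same excess would remain after imputation under missing at random. It does not measure what the fix recovers.

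**What to change.** Replace the exclusion sentence with a rule to this effect: all randomised participants remain in the intention-to-treat set; data collected up to opt-out are used; later outcomes are treated as missing under the stated multiple imputation and, in the sensitivity analysis, as non-use or smoking; data are removed only where a participant withdraws permission to use them; opt-outs and removals are reported by arm and timing.

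The section should also define the difference between stopping participation, stopping follow-up contact and withdrawing permission to use data. The protocol should acknowledge that, for opt-outs with no 2-month outcome, the protection comes from the sensitivity analysis and not from the imputation.

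The cost is a sentence or two in the protocol and a check that the participant information and consent wording agree. The target of 876 does not change, and no new measurements are needed. If participants have already been told that opting out removes their data, that undertaking has to be honoured. The analysis set should then be labelled as modified, with the removals shown by arm.
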